8. STUDY ASSESSMENTS AND PROCEDURES

- Study procedures and their timing are summarized in the [SoA](#). Protocol waivers or exemptions are not allowed.
- Immediate safety concerns should be discussed with the sponsor immediately upon occurrence or awareness to determine if the participant should continue or discontinue study treatment.

- Adherence to the study design requirements, including those specified in the [SoA](#), is essential and required for study conduct.
- All screening evaluations must be completed and reviewed to confirm that potential participants meet all eligibility criteria. The investigator will maintain a screening log to record details of all participants screened and to confirm eligibility or record reasons for screening failure, as applicable. For patients in screening for Cohort B1, the BICR must review screening biopsy, cytology, and imaging prior to registration to confirm diagnosis of CIS alone or with concomitant recurrent Ta/T1 disease and absence of muscle-invasive bladder cancer and extravesical disease.
- Procedures conducted as part of the participant's routine clinical management (eg, blood count) and obtained before signing of the ICD may be utilized for screening or baseline purposes provided the procedures met the protocol-specified criteria and were performed within the time frame defined in the [SoA](#).

Medical history of the participants will be collected per the [SoA](#) as follows:

- Tumor history: Includes history of NMIBC including details of primary diagnosis and treatment history.
 - For Cohorts B1 and B2, detailed information about prior BCG usage (number of doses administered, date of dosing, dose levels, and strain used), disease persistence or recurrence after BCG treatment (including grade and stage) and the date of disease persistence or recurrence.
 - For Cohorts B1 and B2, reasons for subject ineligibility or refusal of radical cystectomy.
- Medical History: Includes history of disease process (eg, staging) other than the cancer under study (active or resolved) and concurrent illness. Includes prior treatments and any current medical treatments for any condition.

8.1. Efficacy Assessments

8.1.1. Clinical Assessments

Cytology and cystoscopy results will be read locally by qualified and experienced study personnel. Data obtained from cystoscopy, cytology, biopsy and imaging (computed tomography [CT] / magnetic resonance imaging [MRI]) will be evaluated locally during the course of the study according to the disease assessment decision algorithm in Section [10.9](#) and will be used for primary analyses in Cohort A and Cohort B2.

Independent reviewers will provide retrospective central assessment of imaging and tumor tissue samples taken during the study for Cohort A. This includes the tumor tissue sample(s) taken from the TURBT supporting the primary diagnosis for the study during the screening period, biopsies or TURBT samples collected at the time of recurrence of high-grade disease,

disease progression, persistence of CIS (applicable only to participants with CIS at randomization), or complete response (applicable only to participants with CIS at randomization), and done after a positive cystoscopy or cytology.

For Cohort B1, independent reviewers will provide central assessment of tumor tissue samples (from the TURBT or biopsies supporting the primary diagnosis for the study), cytology, and imaging during screening for the purposes of eligibility evaluation prior to registration. During treatment, independent reviewers will provide retrospective central assessment of biopsies or TURBT samples collected, as well as cytology, cystoscopy, and imaging results and the BICR assessments will be sent to the sites on a regular basis.

See the Study Manual for process details on sending the tissue sample for blinded independent central review (BICR).

8.1.1.1. Cystoscopy

Cystoscopy should be performed and assessed using the same method and equipment by the same study staff (whenever possible), for the duration of the study, in order to reduce subjectivity across multiple assessments. White light, blue light or narrow-band imaging are allowed in this study and blue light is preferred. Number, size and location of the tumors should be documented.

Disease status will be assessed through cystoscopy conducted at screening, every 12 weeks for 2 years following randomization, and every 24 weeks during the rest of follow-up, and as clinically indicated. Timing of disease assessment is to be fixed according to the calendar (± 7 days) starting with randomization for Cohort A and initiation of study intervention for Cohorts B1 and B2, and should not be adjusted for study intervention dose modifications. Please refer to the Schedule of Activities for disease assessment time points for each Cohort.

Cystoscopy with biopsy is required at the time of recurrence of high-grade disease, disease progression, persistence of CIS (applicable only to participants with CIS at randomization), or complete response (applicable only to participants with CIS at randomization) as described in Section 10.9.

In Cohort A, biopsy for confirmation of complete response for participants with CIS should be performed at the 24 week disease assessment, unless collection at the 12 week disease assessment is routinely performed at the given institution. Please consider that if the bladder biopsy collection at the Week 12 disease assessment fails to confirm CR, the biopsy collection must be repeated at the Week 24 disease assessment. If it is not possible to perform the bladder biopsy collection by the Week 24 disease assessment, biopsies should be collected as soon as possible at the next scheduled disease assessment.

Timing of disease assessment is to be fixed according to the calendar (± 7 days), starting with randomization for Cohort A, and initiation of study intervention for Cohorts B1 and B2, and should not be adjusted for study treatment dose modifications.

For cystoscopy without biopsy, either flexible or rigid cystoscopy may be conducted as per the Investigator's clinical judgement or institutional guidance/preference. Further specifications for the procedure are provided in the Study Manual.

For cystoscopy with biopsy, a full thickness tissue specimen is required to be obtained and Sponsor recommends a rigid cystoscopy.

Cystoscopy results from Cohorts A and B1 provided by the investigator will also be included in the BICR assessment.

Independent pathology reviewers will provide central assessment prior to registration for Cohort B1, and retrospective central assessment of all biopsies for Cohorts A and B1. Refer to the manual for process details on sending the slides for the BICR assessment.

8.1.1.2. Cytology

Urine cytology should be performed using the same methods and equipment for the duration of the study, with results being assessed and adjudicated by the same study staff. This is to reduce subjectivity across multiple assessments.

Disease status will be assessed through urine cytology conducted at screening, every 12 weeks during the first 2 years from randomization, every 24 weeks during the rest of follow-up, and as clinically indicated. Timing of disease assessment should be fixed according to the calendar (± 7 days), starting with randomization for Cohort A, and initiation of study intervention for Cohorts B1 and B2, and should not be adjusted for study treatment dose modifications. Please refer to the Schedule of Activities for disease assessment time points for each Cohort.

Cytology results provided by the investigator will also be included in the BICR assessment for Cohort A. For Cohort B1, urine cytology specimens will be included in the BICR assessment.

Cytology results are defined as the following:

1. Positive - if indicative or suggestive of malignant cells:
 - High-grade urothelial carcinoma
 - Suspicious for high-grade urothelial carcinoma
2. Negative if NOT indicative or suggestive of malignant cells:
 - Negative for high-grade urothelial carcinoma cells
 - Presence of low-grade urothelial carcinoma cells
 - Atypical urothelial cell not abnormal enough to be considered as cancerous
3. Indeterminate: unsatisfactory sample.

8.1.1.3. Imaging

CT or MRI or urogram of the abdomen and pelvis/urinary tract are the recommended imaging modalities. Other areas may be scanned as clinically indicated. Imaging should be performed with contrast agents unless contraindicated for medical reasons. The same imaging technique used at screening will be employed in the tumor assessments conducted on study.

For Cohort B1, disease status will be assessed through imaging at screening, every 24 weeks for 2 years after initiation of study intervention. Imaging will be performed until persistence of CIS, recurrence of high-grade disease or disease progression, consent withdrawal, lost to follow-up, EOT, or death. Additional imaging may be performed as clinically indicated. For Cohort A and Cohort B2, imaging is done as clinically indicated.

Guidance for integration of imaging in the disease assessment are provided in the disease assessment decision algorithm in Section [10.9](#).

Independent reviewers will provide central assessment prior to registration for Cohort B1, and retrospective central assessment of all imaging for Cohorts A and B1. Refer to the manual for process details on sending the scans for the BICR assessment.

8.1.2. Patient Reported Outcomes (PROs)

All PRO questionnaires will be administered electronically and will be completed during the visit prior to any other clinical assessments and study procedures, with the exception of the PTAB which will be completed immediately after the study intervention. If laboratory assessments are done on a date prior to the main visit date, PROs may be completed as the first assessment at the main visit. PROs will be administered in following order: EORTC QLQ-C30, EORTC NMIBC24, EQ5D5L, PGIS, PGIC, TSQ, and PTAB.

As of 12 September 2022, PROs will not be required for Cohort B1 and B2 participants.

8.1.2.1. EORTC QLQ-C30

The EORTC QLQ-C30 is a well-known, validated and self-administered PRO.^{[45,46](#)} The EORTC QLQ-C30 is a 30-question survey, which can be grouped into 5 functional domain subscales, including a physical functioning subscale, a role functioning subscale, an emotional functioning subscale, a cognitive functioning subscale and a social functioning subscale. Higher scores on the functional domains are indicative of higher levels of functioning. Oncology related symptoms assessed by the EORTC QLQ-C30 include fatigue (3 items), pain (2 items), nausea and vomiting (2 items), and dyspnea, insomnia, appetite loss, constipation, diarrhea, and financial impact (1 item each). Higher scores are reflective of a greater presence of symptoms.

8.1.2.2. EORTC QLQ-NMIBC24

The EORTC QLQ NMIBC24 is a PRO developed and tested by the EORTC group specifically for patients with non-muscle invasive bladder cancer.^{[47](#)} The NMIBC24 has 24 items which can be grouped into 6 subscales: urinary symptoms (7 items), malaise (2 items),

future worries (4 items), bloating/flatulence (2 items), sexual functioning (2 items), and male sexual issues (2 items). The NMIBC24 also assesses intravesical treatment, female sexual issues, sexual intimacy, risk of contaminating a partner, and sexual enjoyment (1 item each). Higher scores indicate greater impairment, with the exception of the sexual function and sexual enjoyment items, where higher scores indicate better function.

8.1.2.3. EuroQol 5 Dimensions, 5-Level (EQ-5D-5L) and Visual Analog Scale (VAS)

The EQ-5D-5L is a 6-item patient-completed questionnaire designed to assess health status in terms of a single index value or utility score.⁴⁸ There are 2 components, a Health State Profile which has individuals rate their level of problems (none, slight, moderate, severe, extreme/unable) in 5 areas (mobility, self-care, usual activities, pain/discomfort, and anxiety/depression), and a VAS in which participants rate their overall health status from 0 (worst imaginable) to 100 (best imaginable). Published weights are available that allow for the creation of a single summary score. Overall scores range from 0 to 1, with lower scores representing a higher level of dysfunction.

8.1.2.4. Patient Global Impression of Severity (PGIS)

The PGIS is a single-item PRO designed to facilitate an anchor-based methodology for establishing meaningful within person change (MWPC) of other PRO-based endpoints such as the EORTC QLQ-C30 and QLQ-NMIBC24. There are 4 response options, ranging from “none” to “severe”. The instrument is available in Section [10.16.1](#).

8.1.2.5. Patient Global Impression of Change (PGIC)

The PGIC is a single-item PRO designed to assess the participants overall impression of the degree of change they have experienced since the start of study treatment. There are 5 response options, ranging from “much worse” to “much better”. The instrument is available in Section [10.16.2](#).

8.1.2.6. Patient Treatment Administration Burden (PTAB)

The PTAB questionnaire is a 2-item PRO designed to assess, from the participant perspective, any pain associated with the treatment administration and the burden of the amount of time required to complete the treatment administration procedures (1 item each). The PTAB is available in Section [10.16.3](#).

8.1.2.7. Treatment Satisfaction Questionnaire (TSQ)

The TSQ is a 3-item PRO designed to assess participant satisfaction with the study treatments. The TSQ assesses overall satisfaction with the study treatment, number of treatment administrations, and the form of treatment administration (injection into stomach and catheter into bladder) (1 item each). The instrument is available in Section [10.16.4](#).

8.2. Safety Assessments

Planned time points for all safety assessments are provided in the [SoA](#). Unscheduled clinical laboratory measurements may be obtained at any time during the study to assess any perceived safety issues.

8.2.1. Physical Examinations

Physical examinations should be performed according to clinical practice, but will not be recorded in the eCRF. Rather, any abnormalities should be recorded in the eCRF as AEs.

8.2.2. Vital Signs

- Vital signs will be measured as indicated in the [SoA](#). Any abnormalities will be recorded in the eCRF as AEs.
- BP and pulse rate will be assessed in a supine position with a completely automated device. Manual techniques will be used only if an automated device is not available.
- BP and pulse rate should be preceded by at least 5 minutes of rest for the participant in a quiet setting without distractions (eg, television, cell phones).

8.2.3. ECOG Performance Status

Refer to Section [10.10](#) for ECOG Performance Status Criteria. ECOG will be performed per [SoA](#).

8.2.4. Electrocardiograms

Electrocardiogram (12-Lead)

- A single 12-lead ECG tracing (with a 10 second rhythm strip) will be obtained at the time points described in the [SoA](#).
- Generally, baseline and all corresponding time point ECGs should not be collected within 3 hours after food or beverage consumption and should be performed after the participant has rested quietly for at least 10 minutes in a supine position. All 12-lead ECGs should be confirmed by a qualified person at the institution.
- ECGs will be collected prior to dosing of study intervention as indicated in the [SoA](#). When the timing of these measurements coincides with a blood collection, the ECG should be obtained prior to the nominal time of the blood collection, BP, and pulse rate.
- For the purposes of eligibility assessment and general safety monitoring, sites must enter the QTcF value provided by their ECG machine or calculated manually.
- If the QTcF is prolonged (≥ 60 msec from the pre-dose baseline or is > 500 msec), then the ECGs should be reevaluated by a qualified person at the site for confirmation as soon as the finding is made, including verification that the machine reading is accurate. If

manual reading verifies a QTcF of ≥ 60 msec from the pre-dose baseline or is > 500 msec, immediate correction for reversible causes (including electrolyte abnormalities, hypoxia and concomitant medications for drugs with the potential to prolong the QTcF interval) should be performed. In addition, repeat ECGs should be immediately performed hourly for at least 3 hours until the QTcF interval falls below ≥ 60 msec from the pre-dose baseline or is ≤ 500 msec depending on the type of change originally observed. If QTcF interval reverts to less than 60 msec from the pre-dose baseline or is ≤ 500 msec, and in the judgment of the investigator(s) and sponsor is determined to be due to cause(s) other than the study intervention, treatment may be continued with regular ECG monitoring. If in that timeframe the QTcF intervals rise above ≥ 60 msec from the pre-dose baseline or is > 500 msec the study intervention will be held until the QTcF interval decreases to ≤ 60 msec from the pre-dose baseline or is ≤ 500 msec, depending on the type of change originally observed.

- Note: If QTc values remain > 500 msec (or ≥ 60 msec from the pre-dose baseline) for greater than 4 hours (or earlier at the discretion of the investigator); or QTc intervals get progressively longer, the participant should undergo continuous ECG monitoring. A cardiologist should be consulted if QTc intervals do not return to less than 500 msec (or to < 60 msec above the pre-dose baseline) after 8 hours of monitoring (or earlier at the discretion of the investigator).
- Once the QTcF interval decreases to ≤ 60 msec from the pre-dose baseline or ≤ 500 msec, depending on the type of change originally observed, participants may restart the study intervention. If the QTcF interval has still not decreased to ≤ 60 msec from the pre-dose baseline or ≤ 500 msec after 2 weeks (depending on the type of change originally observed), or if at any time a participant has a QTcF interval > 515 msec or becomes symptomatic, the participant will be removed from the study. Additional triplicate ECGs may be performed as clinically indicated.
- Prior to concluding that an episode of QTcF interval prolongation is due to the study intervention, thorough consideration should be given to potential precipitating factors (eg, change in participant clinical condition, effect of concurrent medication, electrolyte disturbance) and possible evaluation by specialist.
- If participant experiences a cardiac or neurologic AE (specifically syncope, dizziness, seizures, or stroke), triplicate ECGs should be obtained at the time of the event.
- In some cases, it may be appropriate to repeat abnormal ECGs to rule out improper lead placement as contributing to the ECG abnormality. It is important that leads are placed in the same positions each time in order to achieve precise ECG recordings. If a machine read QTc value is prolonged, as defined above, repeat measurements may not be necessary if a qualified physician's interpretation determines that the QTc values are in the acceptable range.

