7. DISCONTINUATION OF STUDY INTERVENTION AND PARTICIPANT DISCONTINUATION/WITHDRAWAL

7.1. Discontinuation of Study Intervention

For participants in Cohort A, it may be necessary for a participant to permanently discontinue one of the two study interventions. In that case, please note that the participant will still continue with the other study intervention. If it is necessary for the participant to permanently discontinue both PF-06801591 and BCG, the participant will remain in the study and move into the post-treatment follow-up period to allow for an adequate evaluation of the study objectives based on the prespecified estimands.

Note that permanent discontinuation of study treatment does not represent withdrawal from the study.

Participants may withdraw from study treatment at any time at their own request, or they may be withdrawn at the discretion of the investigator or sponsor for safety or behavioral reasons, or the inability of the participant to comply with the protocol-required schedule of study visits or procedures at a given study site.

Reasons for withdrawal of study treatment in Cohorts A, B1, and B2 may include:

- Completion of study treatment (25 cycles for Cohort A, Arms A, B and C, and Cohort B1, and 17 cycles for Cohort B2)
- Participants with CIS at baseline who do not achieve a CR within 6 months of initiating study intervention will be withdrawn from study treatment
- Recurrence of high-grade disease (Section 10.9) or progression of disease
- Global deterioration of health status requiring discontinuation of study treatment
- Unacceptable toxicity
- Pregnancy
- Significant protocol violation
- Lost to follow-up
- Participant refused further treatment
- Study terminated by sponsor
- Death

Discontinuation of study treatment for abnormal liver function should be considered by the investigator when a participant meets one of the conditions outlined or if the investigator believes that it is in best interest of the participant. See Section 10.6 for details.

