If a clinically significant finding is identified (including, but not limited to changes from baseline in QT interval corrected using Fridericia's formula [QTcF] after enrollment), the investigator or qualified designee will determine if the participant can continue in the study and if any change in participant management is needed. This review of the electrocardiogram (ECG) printed at the time of collection must be documented. Any new clinically relevant finding should be reported as an AE. Refer to Section 8.2.4 for detailed information on criteria for holding or discontinuing study treatment in the case of change in QT interval.

See the [SoA](#) for data to be collected at the time of intervention discontinuation and follow-up and for any further evaluations that need to be completed.

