7.2. Participant Discontinuation/Withdrawal from the Study

A participant may withdraw from the study at any time at his/her own request. Reasons for discontinuation from the study include the following:

- Refused further follow-up
- Lost to follow-up
- Death
- Study terminated by sponsor

If a participant withdraws from the study, he/she may request destruction of any remaining samples taken and not tested, and the investigator must document any such requests in the site study records and notify the sponsor accordingly.

If the participant withdraws from the study and also withdraws consent (see Section 7.2.1) for disclosure of future information, no further evaluations should be performed, and no additional data should be collected. The sponsor may retain and continue to use any data collected before such withdrawal of consent.

Lack of completion of all or any of the withdrawal/early termination procedures will not be viewed as protocol deviations so long as the participant's safety was preserved.

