8.2.6. Survival Follow-up

To collect OS data for Cohort A participants only, once participants enter the survival follow-up period, they will be contacted by telephone every 12 weeks (± 7 days) until consent withdrawal, lost to follow-up, death, or end of the study (5 years after last participant randomized to Cohort A). If the participant is seen in the clinic during the window of time that a scheduled telephone call is to be made to collect survival data, then the clinic visit may replace the survival telephone call. For Cohort A participants only, any subsequent anti-cancer therapy (including cystectomy), if administered, will be documented and recorded for participants who discontinue the study intervention and continue in post-treatment safety follow-up until recurrence of high-grade disease or progression of disease. The sponsor may request that sites complete additional survival follow-up to facilitate planned analyses as needed.

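### Protocol Section 8.2.4 removes participants who meet a QTcF trigger from the study, although Sections 7.1 and 8.2.6 and the EFS and OS estimands require follow-up to continue

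*Protocol*

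**What the plan says.** Most of protocol Section 8.2.4 (Electrocardiograms) concerns holding and restarting the study drug when QTcF is prolonged. Its last step goes further. If QTcF has not returned to the threshold after 2 weeks, or is above 515 msec at any time, or the participant "becomes symptomatic, the participant will be removed from the study". The step is automatic and does not depend on consent.

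Other parts of the protocol read differently:

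- **Section 7.1** says that a participant who must stop both drugs "will remain in the study and move into the post-treatment follow-up period", and that "permanent discontinuation of study treatment does not represent withdrawal from the study". It refers to 8.2.4 for "criteria for holding or discontinuing study treatment in the case of change in QT interval". For a clinically significant finding, including a QTcF change, it also says that the investigator or designee "will determine if the participant can continue in the study".
- **Section 7.2** begins "Reasons for discontinuation from the study include the following" and names refusal of follow-up, loss to follow-up, death and termination by the sponsor.
- **Section 8.2.6** runs survival calls in Cohort A "until consent withdrawal, lost to follow-up, death, or end of the study".
- **Section 9.1.1.1** defines the EFS and OS estimands on all randomized participants, irrespective of tolerability and of time on treatment.

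**The concern.** The estimands treat a tolerability event as something that happens during follow-up, not as a reason to stop observing. Read literally, 8.2.4 does the opposite. A QTcF event would end cystoscopy and cytology, survival calls, and the 30-, 60- and 90-day safety visits that Section 4.1.1 sets for all participants. The participant would not have withdrawn consent, and those with marked QT prolongation are people whose safety follow-up matters.

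The wording also binds sites. Protocol Section 8 allows no waivers, and SAP Section 6.5.2.2 reports as deviations participants who meet withdrawal criteria and are not withdrawn. A site that sensibly kept such a participant in follow-up could therefore be listed as deviating.

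The SAP has no censoring category for removal by rule. Such a participant could be reported as still under observation for EFS.

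**Working it through.** **Step 1. The provisions side by side.** The plan attaches no figure to this rule, so the main check is textual.

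| Place | Effect of a QTcF trigger or tolerability event |
|---|---|
| Protocol 8.2.4, last step | Automatic removal from the study |
| Protocol 7.1, stopping both drugs | Treatment ends, follow-up continues |
| Protocol 7.1, reference to 8.2.4 | 8.2.4 governs treatment only |
| Protocol 7.1, clinically significant findings | Investigator judges whether the participant continues |
| Protocol 7.2 | No ECG or safety reason named, but the list is not exhaustive |
| Protocol 8.2.6 | No ECG reason to end survival calls |
| Protocol 9.1.1.1 | Estimands apply irrespective of tolerability |

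No other provision makes removal automatic. The investigator's discretion in 7.1 also conflicts with an automatic rule.

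**Step 2. What the SAP would do with a removed participant.**

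- *EFS censoring date (Table 11).* Given an adequate baseline, a participant with no event is censored at the last adequate assessment, whatever the reason. The reason label does not change the primary EFS result.
- *EFS censoring reason (Table 12).* A removed participant with an adequate post-baseline assessment, and no entry for consent withdrawal or loss to follow-up, falls to level 6, the residual category for those still being observed. Level 5 needs both no adequate post-baseline assessment and either an end-of-follow-up page or end-of-treatment pages stating no continuation. Without those pages, a participant with no adequate assessment also reaches level 6.
- *OS censoring reason (Table 16).* The same participant counts as lost to follow-up once last contact is more than 365 days before the cut-off. Table 12 has no such rule.
- *Informative-censoring analysis (Section 6.2.2.3).* Imputation covers loss to follow-up, consent withdrawal and no adequate post-baseline assessment, so level 6 is left out. The analysis runs only if dropout is imbalanced between arms.

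**Step 3. Illustration for one removed participant.** Suppose removal at Cycle 6 Day 1, the last scheduled on-treatment ECG in Cohort A (protocol Section 1.3). Assume the 22-month accrual in SAP Section 5.1.1, survival follow-up to 5 years after the last randomization, and an EFS cut-off about 3 years after it.

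- Time of removal: 5 × 28 = 140 days; 140/365.25 = 0.383 years.
- Survival follow-up lost: 5 − 0.383 = 4.62 years (last randomized); 5 + 22/12 − 0.383 = 6.45 years (first randomized).
- Disease follow-up lost before the EFS cut-off, if no event would have occurred first: 3 − 0.383 = 2.62 years; 3 + 22/12 − 0.383 = 4.45 years.
- Deaths: 150 expected OS events / 1056 randomized = 0.142; 1056/150 = 7.04. About one death is missed per 7 participants removed, if every death falls after removal and none is recovered.

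These are illustrations, not bounds. ECGs are also done earlier, and later when clinically indicated. The 22 months is a planning assumption.

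**Step 4. Why no power loss is claimed.** The 261 EFS events (174 per comparison) are projected from blinded observed accrual. Amendment 5 is dated 17 June 2024, 214 days (7.0 months) after Cohort A treatment ended on 16 November 2023. Any removals are already reflected in that accrual. For OS, no count of removals exists from which to compute a loss.

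**The case against.** The strongest reply is that the rest of the protocol already settles the meaning. Section 7.1 treats 8.2.4 as treatment criteria, keeps participants who stop both drugs in the study, and says that stopping is not withdrawal. A sensible site would have read it that way. Section 7.2 adds little, because its list is introduced as non-exhaustive. The trigger operates during dosing, which is over in Cohort A, and Cohorts B1 and B2 no longer have disease or survival follow-up after end of treatment. The SAP already plans outputs that could show any case.

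Most of this stands, and it is why the point is minor. It does not make the sentence correct: 8.2.4 is an operative instruction, and it says something different from the section that cites it.

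A reader might infer more than the documents support:

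- *That participants were removed and the EFS or OS comparison is biased.* No removal is documented, and no QT events are given by arm, so whether such censoring would be informative cannot be judged.
- *That Table 12 would necessarily mislabel them.* That depends on the disposition code chosen, and the eCRF options are not in the documents.
- *That only removals after the Week 12 assessment can reach level 6.* The page condition at level 5 defeats this, and unscheduled assessments also count (SAP Section 5.2.9).
- *That the missing contact-gap rule in Table 12 results from 8.2.4.* It would affect anyone who silently leaves follow-up.

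**Conclusion.** The last step of Section 8.2.4 is wrong as written, and the matter is minor. It contradicts Sections 7.1 and 8.2.6 and the estimands. Treatment discontinuation was almost certainly intended.

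Confidence is high for the wording conflict. It is much lower for any effect on results, which would require that someone was actually removed and that survival status was not recovered. The number affected is unknown and probably very small. Even then, the primary EFS censoring date would not depend on the reason label. Only the reported censoring reasons and a conditional sensitivity analysis could be wrong, together with any EFS events or deaths that went unobserved.

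**What to change.** 1. **Wording.** In the last step of 8.2.4, replace removal from the study with permanent discontinuation of study treatment and entry into post-treatment safety, disease and survival follow-up under Section 7.1.
2. **Look-back.** Use the planned disposition output and listing (SAP Section 6.5.2.1) and the notable-ECG listing (SAP Section 6.6.6) to identify, by arm, any Cohort A participant whose follow-up was stopped under this rule.
3. **If any are found.** Recover survival status before the final OS analysis. Section 8.2.6 gives one route, with consent: "The sponsor may request that sites complete additional survival follow-up to facilitate planned analyses as needed". Section 7.2.1 gives another, through public sources where local law allows. Treat these participants as dropouts in the Table 12 reasons, not as level 6, and include them in the informative-censoring analysis if it is run.
4. **If none are found.** Say so in one sentence of the study report. No SAP change is then needed.

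The cost is one phrase in the protocol and one query of outputs already planned. The phrase can go with the next amendment or clarification letter. Survival calls and relabelling arise only if a case is found. Time is sufficient: SAP version 8 is dated 10 December 2024 and the final OS analysis falls about 16 November 2026, 706 days or 23.2 months later.
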